#### **6.2.4 Randomization Procedure**

Participants will be randomized after attending their Baseline Visit 2 according to the block (by sex) randomization scheme developed by the study statistician. An unblinded study staff member will call the participant and, after reconfirming their willingness to be randomized, will inform them of their group assignment and their planned intervention start date and time. Randomization date will be documented and will occur within approximately 12-16 weeks of the initial Screening Visit, but within approximately 4 weeks of their intervention start date.

#### **6.2.5 Six-month Follow-up Visit 1 (FV1)**

There will be one interim follow-up visit after approximately 22-26 weeks of intervention for each group. All assessments during this visit will be conducted by assessors blinded to the randomized group assignment of the participant. Participants will come in fasting and will have the following assessments:

- Vital signs and waist circumference
- Blood for archival storage and the expanded 25 panel biomarker assessment funded through the NCI supplement. Venous blood samples will be

collected in the morning following a fast of at least 10 hours. Total blood volume collected is estimated at 36.5 ml (~2 Tbsp), including:

- serum
- plasma (EDTA and plasma citrate)
- Urine Collection for storage
- Siteman online cancer risk assessment (117) & Cancer Screening Questionnaire (Both may be done at a later visit or by phone for those who have completed all visits).

#### **6.2.6 Nine-month Follow-up Visits 2 and 3**

There will be two follow-up evaluation visits after approximately 34-40 weeks of intervention for each group. All assessments during these visits will be conducted by assessors blinded to the randomized group assignment of the participant.

##### **9-Month Follow- Visit 2 (FV2) - Fasting**

- Vital signs with waist measurement
- Blood lipids, insulin, HbA1c, CBC, CMP, HbA1c, TSH
- Fasting blood draw and urine collection for biomarker assays, DLW, d3cr and biospecimen archive: see Baseline Visit for detail, but with lower sample volume for archive. Total blood volume collected is estimated at 85.5 ml (~6 Tbsp), including:
  - serum
  - plasma (EDTA and plasma citrate)
  - whole blood in ACD or CPT tubes for cell and DNA isolation
  - blood in RNA stabilizer tube
- Resting Energy Expenditure
- 24-hour Dietary Recalls (ASA24)
- Doubly-labeled water (DLW Dosing) and urine collection for TEE
- Physical activity energy expenditure using ActivPAL
- DXA (Whole Body, Hip & Lumbar Spine)
- CES-D
- MoCA
- Power of Food Scale
- Weight Efficacy Lifestyle Questionnaire
- Perceived Stress Scale
- Delayed Discounting
- Food Craving Inventory & Emotional & Uncontrolled Eating
- Walking Self-Efficacy
- SF-36
- PROMIS 13a (FACIT) Fatigue Scale, Pittsburgh Fatigability Scale, and Pittsburgh Sleep Quality Index
- PROMIS Interest in Sexual Activity questionnaire
- Interim Medical Events / Adverse Events
- STOP Questionnaire

- Epworth Sleepiness Scale

#### 9-Month Follow-up Visit 3 (FV3): Final Evaluation

- Final Medical Events / Medication Updates / Adverse Events
- Doubly-Labelled Water (Final Urine Collections)
- Physical Activity Energy Expenditure (Return of ActivPAL device)
- Short Physical Performance Battery (and expanded SPPB)
- Fast 400 meter walk
- Grip strength
- *Participant evaluations of CR or TRE.* We will ask participants to list any positive or negative outcomes that they associate with either the CR or TRE intervention. Participants are limited to identifying a maximum of 5 outcomes in each category (they can report none). For each outcome listed, they are asked to rate how important each one was to either adhering or not adhering to the goals of the intervention.
- *Participant Satisfaction.* Participants will be asked to rate a series of questions using a Likert scale and complete a series of open-ended questions assessing the acceptability of each key intervention component they received using questions modeled on our previous work and will assess their willingness to continue the intervention for longer durations (i.e., 4yrs).

We may contact some or all participants roughly one year after the end of their participation to ask about their weight and if it's changed in the last year. This will be optional for participants and will not be considered outcome data.

#### **6.2.7 Assessments conducted during intervention:**

- *Continuous Glucose Monitoring.* Continuous glucose monitoring (CGM) will assess time in the fasting state in the TRE group using a continuous glucose monitor (G6 Pro, Dexcom) at approximately 3 months (weeks 8-12) and 8 months (weeks 28-32). The CGM records interstitial glucose concentrations every 5 minutes for up to 10 days and will be in blinded mode so the participant cannot see their values. Although it measures glucose levels in the interstitial fluid – and not blood glucose levels – it has been demonstrated to be accurate in the comparison with capillary blood glucose results with the correlation between CGM and capillary blood glucose results of 0.95 (104, 105). The CGM is placed on the lower abdomen using a one-touch applicator by an unblinded study staff member.
- *Ecological Momentary Assessments of Hunger, Desire to eat and Anxiety* (6 assessments during 7 days of months 1, 4 and 7): Within the mHealth *Companion App* we will prompt participants to complete six brief (<60 seconds) ecological momentary assessments (EMAs) each day (waking, late morning, lunch, afternoon, dinner, bedtime) of hunger, desire to eat, and anxiety during 7 days of months 1, 4 and 7. Participants note their hunger in response to the question “to

what extent are you hungry right now?", with responses ranging from "no hunger" to "extreme hunger". Participants note their desire to eat in response to the question "to what extent do you have a desire to eat right now?" with responses ranging from "no desire" to "extreme desire". Anxiety will be rated in response to the question "how anxious do you feel right now?" with responses ranging from "no anxiety" to "extreme anxiety". All responses are provided using a slider with values (which are hidden to the participant) ranging from 0-1000 to simulate a continuous slider.

## **7 SAFETY ASSESSMENTS**

The safety of HALLO-P's participants is of paramount importance and will be monitored upon enrollment in the study. Enrollment starts after a participant gives verbal consent to be phone screened. The HALLO-P interventions are generally regarded as safe, as the entry criteria are based on the public health-based indications for weight loss.

Nevertheless, the study's entry criteria are designed to screen-out those for whom CR or TRE may have potentially adverse effects. These include: a history of eating disorders, moderate - severe anemia, uncontrolled hypertension, uncontrolled thyroid disease, osteoporosis, a high risk of fracture, and uncontrolled diabetes.

### **7.1 Specification of Safety Parameters**

*Exclusion due to potential safety concerns:*

- Osteoporosis (self-report, osteoporosis medication, or DXA t-score  $\leq -2.5$  on total hip and/or femoral neck scan)
- Self-Report of Type 1 diabetes, use of insulin
- Self-Report of a new diagnosis of Type 2 diabetes (within one year) or newly discovered (elevated HbA1c  $\geq 6.5$  at screening), use of some medications used to treat diabetes or HbA1c  $>7.5\%$

*Exclusions for Conditions associated with dietary management that might conflict with a study intervention. These can be rechecked two weeks later if needed to confirm exclusion.*

- Uncontrolled hypertension ( $>160$  systolic OR  $>100$  mmHg diastolic)
- Dialysis or abnormal kidney function (eGRF  $<30$  mL/min/1.73 m $^2$ )
- Liver disease or abnormal liver function (ALT levels 2 times above normal)
- Moderate-Severe anemia (Hb  $<11$ g/dL)
- Potassium or sodium above or below normal limit
- Uncontrolled thyroid disease (hypo/hyper) or requiring recent (past 3 months) adjustments in thyroid hormone supplementation or TSH  $<0.45$  or  $>4.5$  uIU/mL

### **7.2 Methods and Timing for Assessing, Recording, and Analyzing Safety Parameters**

All participants will be queried for safety events at each assessment visit after the screening visit, and on a monthly basis during intervention at the individual sessions. Both open-ended questions and pre-defined questions of symptoms relevant to common risks of the assessments and

interventions will be asked. All AEs reported to study staff (including those not discovered during the monthly queries) will be recorded using the study's Adverse Event Reporting Form.

AEs and SAEs will be coded and summarized using MedDRA coding and intervention group, with the number of participants and percentage reporting the event. The study investigators, except for [name] and [name], will be blinded to review of AEs/SAEs by intervention group. Drs. [name] and [name] will review AEs on a quarterly basis and the study mPIs will review AEs blinded to intervention status.

### **7.3 Adverse Events and Serious Adverse Events**

All participants will be queried at each assessment visit regarding any change in health or physical status using the Health Status Questionnaire and any AEs will be reported using the IRB-approved Adverse Event Reporting form and the running medication log will be updated, as needed. Expected events (signs and symptoms) will be assessed monthly by unblinded interventionist. All AEs reported to study staff, including unsolicited AEs (not including those discovered during the monthly queries) will be recorded using the study's Adverse Event Reporting Form. Study staff will try to match-up unsolicited AEs with events reported per scheduled assessment. Those that do match will be handled through the routine system will be followed and flagged, and reported separately when AEs are summarized. A summary of the expected AEs will be reported from the signs and symptoms questionnaire, but an AE form and evaluation is not required for these common events.

The AE form includes a section for classifying the AEs: 1) Severity, 2) Expectedness (Expected—event is known to be associated with the intervention or assessment activity or Unexpected—not expected or consistent with known information regarding the activity), and 3) Relatedness to the study intervention (Definitely Related, Possibly Related, or Not Related).

Double capture of AEs (e.g., a participant providing an unsolicited report and a second report of the same event at an ascertainment visit) is identified through assigning unique event numbers to AEs, which are then used to link repeated reports within the data capture system. Filtering out of repeated capture of the same event is done during report generation

**7.3.1 Adverse Event (AE):** Any untoward or unfavorable medical occurrence in a clinical research study participant, including any abnormal sign (e.g., abnormal physical exam or laboratory finding), symptom, or disease, temporally associated with the participants' involvement in the research, whether or not considered related to participation in the research. These will be assessed at each clinic visit and monthly during intervention

The occurrence of an adverse event (AE) or serious adverse event (SAE) may come to the attention of study personnel during study visits and interviews of a study participant presenting for medical care, or upon review by a study monitor.

All AEs not meeting the criteria for SAEs will be captured on the appropriate case report form (CRF). Information to be collected includes event description, time of onset, qualified medical professional's assessment of severity, relationship to study product (assessed only by those with the training and authority to make a diagnosis), and time of resolution/stabilization of the event. All AEs occurring while on study must be documented appropriately regardless of relationship. All AEs will be followed to adequate resolution.

**7.3.2 Serious Adverse Event (SAE):** Any adverse event that:

- Results in death
- Is life threatening, or places the participant at immediate risk of death from the event as it occurred
- Requires or prolongs hospitalization
- Causes persistent or significant disability or incapacity
- Is another condition which investigators judge to represent significant hazards

**7.3.3 Unanticipated Problem (UP):** Any incident, experience, or outcome that meets all of the following criteria:

- unexpected, in terms of nature, severity, or frequency, given (a) the research procedures that are described in the protocol-related documents, such as the IRB-approved research protocol and informed consent document; and (b) the characteristics of the study population;
- related or possibly related to participation in the research (in this guidance document, possibly related means there is a reasonable possibility that the incident, experience, or outcome may have been caused by the procedures involved in the research);
- suggests that the research places participants or others at a greater risk of harm (including physical, psychological, economic, or social harm) than was previously known or recognized.

#### **7.3.4 Severity of Event**

All Adverse Events will be classified according to severity according to the following:

- Mild: Awareness of signs or symptoms, but easily tolerated and are of minor irritant type causing no loss of time from normal activities. Symptoms do not require therapy or a medical evaluation; signs and symptoms are transient.
- Moderate: Events that introduce a low level of inconvenience or concern to the participant and may interfere with daily activities but are usually improved by simple therapeutic measures; moderate experiences may cause some interference with functioning.
- Severe: Events interrupt the participant's normal daily activities and generally require systemic drug therapy or other treatment; they are usually incapacitating.

#### **7.3.5 Expectedness**

All AEs will be assessed as to whether they were expected to occur or unexpected, meaning not anticipated based on current knowledge found in the protocol and include:

- Unexpected - nature or severity of the event is not consistent with information about the condition under study or intervention in the protocol, consent form, product brochure, or investigator brochure.
- Expected - event is known to be associated with the intervention or condition under study.

#### **7.3.6 Relationship to Study Intervention**

The study's physician or medical officer will assess the relationship of all AEs to study intervention or study participation. Based on clinical judgement and complete description of the event he will determine if the event is:

- *Definitely Related* – The adverse event is clearly related to the investigational agent/procedure – i.e., an event that follows a reasonable temporal sequence from administration of the study intervention, follows a known or expected response pattern to the suspected intervention, that is confirmed by improvement on stopping and reappearance of the event on repeated exposure and that could not be reasonably explained by the known characteristics of the subject's clinical state.
- *Possibly Related* – An adverse event that follows a reasonable temporal sequence from administration of the study intervention follows a known or expected response pattern to the suspected intervention, but that could readily have been produced by a number of other factors.
- *Not Related* – The adverse event is clearly not related to the investigational agent/procedure – i.e., another cause of the event is most plausible; and/or a clinically plausible temporal sequence is inconsistent with the onset of the event and the study intervention and/or a causal relationship is considered biologically implausible.

#### **7.4 Reporting Procedures**

Any major AE, i.e., any serious injury, including all SAEs, will be recorded and reported to the mPIs immediately after completing any and all actions that are necessary to protect the subject's health and safety. Minor AEs will be recorded and reported to the PIs on at the regular PI meetings. A description of the event, and the date and location of the event will be recorded on the AE Reporting Form, which will be kept in the participant's research file. The mPIs and the Study Physician ([name]) will meet quarterly to review all reported events and these will be compiled and reported in aggregate to the DSMB.

Within 48 hours of notification of any SAE that is unexpected and related (death within 24 hours), the contact PI ([name]) will report the event to the WFSM Institutional Review Board (IRB), the NIH Program Officer and the Chair of the DSMB through channels specified by the NIH or its contractors.

Any unanticipated problem involving risks to study participants or others will be reported within 48 hours to the NIA and will be forwarded to OHRP within two weeks of the event.

Any medical condition that is present at the time that the participant is screened will be considered as baseline and not reported as an AE. However, if the study participant's condition deteriorates at any time during the study, it will be recorded as an AE.

Changes in the severity of an AE will be documented to allow an assessment of the duration of the event at each level of severity to be performed. AEs characterized as intermittent require documentation of onset and duration of each episode.

The study staff will record all reportable events with start dates occurring any time after informed consent is obtained until the last day of study participation, with follow-up of any active events. At each study visit, the investigator will inquire about the occurrence of AE/SAEs since the last visit. Events will be followed for outcome information until resolution or stabilization.

## **7.5 Safety Monitoring**

Safety will be monitored by an NIA appointed Data and Safety Monitoring Board (DSMB). The DSMB will act in an advisory capacity to the NIA Director to monitor participant safety, data quality and progress of Nutritional Interventions Planning Project. Meetings of the DSMB will be held regularly (e.g., every six to nine months) at the call of NIA or the DSMB Chair. The NIA staff will be present at every meeting. An emergency meeting of the DSMB may be called at any time by the Chair or the NIA, should participant safety questions or other unanticipated problems arise.

DSMB meetings will consist of open, closed and optional executive sessions, all closed to the public because discussions may address confidential participant data. The study PI and key staff members, DSMB members and authorized NIA staff attend the open sessions. Discussions at these sessions focus on the review of the aggregate data, conduct and progress of the study, including participant accrual, protocol compliance, and problems encountered. Data by treatment group are not presented in the open session.

The closed session will be attended by unmasked study staff, the DSMB members and the NIA PO or designee, but not by the NIA Project Scientist(s). The NIA PO attends the closed and open sessions as an observer, not as a DSMB member, to answer any policy or administrative questions the DSMB members may have. The primary objective of the closed sessions is to review data by study group. To ensure participants safety and well-being, DSMBs for NIA-funded trials are usually required to review safety data by the actual treatment group. The timing of unmasking of the treatment groups is determined by the DSMB. In many instances, safety data could also be the outcome data. Therefore, the unmasked Boards no longer review and provide recommendations to NIA on any, but safety-related protocol changes. All other protocol modifications are subject to review by the masked working groups of the DSMBs. DSMBs' working groups are appointed by NIA and provide their recommendations to NIA Director who makes decisions about whether to approve or decline proposed modifications.

If necessary, an executive session may be requested by the DSMB and will be attended only by voting DSMB members. The NIA Program Officer or designee is not permitted to attend the executive sessions.

## **8 INTERVENTION DISCONTINUATION**

There are no specific events that would lead to intervention discontinuation.

Participants may temporarily discontinue participation due to intercurrent illnesses. In this case, participants will be asked to restart the intervention upon clearance from their primary care provider.

Participants may withdraw voluntarily from participation in the study at any time and for any reason. Participants will continue to be followed, with their permission, even if the study intervention is discontinued. These participants will be invited to participate in the 6-month and 9-month visits.

Participant who drop from the study after randomization will not be replaced.

## **9 STATISTICAL CONSIDERATIONS**

### **9.1 General Design Issues**

As suggested by multiple authors (106-108), the design and sample sizes for our HALLO pilot study have been chosen to focus on the feasibility of the design of the targeted full-scale study, rather than on power for hypothesis testing between groups.

During the HALLO pilot, we target the enrollment of approximately 100 participants meeting the inclusion/exclusion criteria to one of three intervention arms 1) 20% CR delivered in-person; 2) 20% CR delivered remotely via video conferencing; and 3) 8-hour TRE with *ad libitum* calorie intake for the first 3 waves (66pts) and the fourth wave will randomize ~24 pp to one of two intervention arms including 20% CR delivered remotely and 8-hour TRE groups. We anticipate randomizing 22:34:34 participants with fewer participants being in the in-person CR group since our group (and others) has more experience with that intervention. From those randomized, we anticipate approximately 20:30:30 participants to complete both pre-and post-measures at 9 months. Data from the enrollment process will be used to refine recruitment criteria, estimate recruitment yields, and test and refine intervention approaches. The pilot will inform three design benchmarks: **a)** The degree of sustained CR (**Benchmark 1**): CR > 10% at 9 months; **b)** TRE sustainability (**Benchmark 2**): At least 75% of participants eating within window on >80% of days; and **c)** **Benchmark 3**: Retention > 85% at 9 months.

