### **Sample Size and Population**

The HALLO-P target population is older adults with an indication for weight loss for whom participation is feasible and safe. Approximately to one-hundred participants will be randomized to the three study arms in a 1:1:1 ratio for the first 66 participants. The remaining participants enrolled will be randomized with equal probability to the remote CR and TRE groups. Randomization is stratified by sex.

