Participants who are eligible after the phone screen will be scheduled for an in-person screening visit. A trained study examiner will obtain full informed consent to participate in the study before any data collection. The informed consent form (ICF) obtains information describing both the screening and all other study procedures, including the intervention. The examiner will again describe the study and the requirements for participation, review the informed consent form in detail with the participant, and address any participant questions. Once the participant has had their questions addressed the participant will sign the informed consent and receive a copy for their records. The original signed consent will be placed in the participant's study file. Participants are considered enrolled in the study after providing consent, but do not count towards the goal of ~100 until randomized.

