**Benchmark 2.** We will estimate the proportion of individuals consuming calories within the 8-hour window (+/- 30 min) on 80% of days (i.e., each participant will receive a yes/no categorization as to whether they consumed calories within the window on > 80% of days) based on participants' self-report of first and last meal/snack times. If feasible, this calculation will also be performed using data from continuous glucose monitors. If  $\geq 75\%$  of individuals are compliant at this level, we consider it reasonable to consider that TRE within the window chosen could be sustained for a longer-term trial. With  $N=30$  participants in this group, if the observed sample proportion is 87% or above, the lower bound on the Clopper-Pearson exact 90%, one-sided confidence interval will exclude retention values of 75% or below (112). Here again, in the presence of a positive ICC for TRE 8-hour adherence, there will be an inflation in variance of the mean which will translate into needing observed sample proportions > 87% to exclude a value of 75% or below.

For **Benchmark 3**, we target  $\geq 85\%$  retention in each intervention group based on completion of the 9-month follow-up exam. If the observed sample proportion is 90% or higher ( $N=81/90$ ), Clopper-Pearson exact 90%, one-sided confidence interval will exclude retention values of 85% or below. In the presence of a large, positive ICC for dropout, there will be an inflation in variance of the mean which will translate into needing an observed proportion > 90% to exclude values of ~85% or below.

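### The Benchmark 3 retention figure is off by one completer (81/90 does not exclude 85%; 82/90 does), and the stated total of about 100 does not match the 90 used in the allocation

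*Combined protocol and SAP*

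**What the plan says.** **Total.** Section 9.1 says "we target the enrollment of approximately 100 participants", and the Précis says "Approximately to one-hundred participants will be randomized to the three study arms". Sections 1.1, 3 and 5.1 also give about 100. Section 4.3 makes clear that the number counts randomised people: those who have consented "do not count towards the goal of ~100 until randomized".

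**Breakdown.** Section 9.1 splits the sample by wave, "for the first 3 waves (66pts) and the fourth wave will randomize ~24 pp", and by arm, "We anticipate randomizing 22:34:34 participants". It expects about 20:30:30 to have both baseline and 9-month measures.

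**Benchmark 3.** Section 9.2 sets a retention target of at least 85% in each intervention group. It then gives one pooled illustration, beginning "If the observed sample proportion is 90% or higher" and written as 81/90. At that proportion, it says, the Clopper-Pearson exact one-sided 90% interval rules out 85% and anything lower. Section 9.5.1 names the same method and level for the analysis. Unlike Benchmarks 1 and 2, it gives no 80% alternative there.

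**The concern.** Retention is one of three primary feasibility outcomes, and section 9.2 tells the reader what observed retention would be convincing. If that figure is wrong by the plan's own method, readers are given a target slightly easier than the interval will allow. The total matters because the evaluable numbers behind Benchmarks 1 and 2 (about 30 in each larger arm) follow from 34 per arm, which belongs to a trial of 90. A reader who takes the headline of 100 cannot tell which size the benchmark figures describe.

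**Working it through.** **1. The total**

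- By wave: 66 + 24 = 90.
- By arm: 22 + 34 + 34 = 90. This agrees with the wave sizes: 66/3 = 22 per arm, and 24/2 = 12 more in each of two arms gives 34.
- Benchmark 3 denominator: 90.

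Three figures give 90 against a stated total of about 100. Consented versus randomised cannot explain the gap, because section 4.3 counts only randomised participants.

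**2. Method, checked on a figure that reproduces**

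The Clopper-Pearson one-sided 90% lower limit for x of n is the 0.10 quantile of a Beta(x, n − x + 1) distribution. Equivalently, the limit exceeds p0 when P(X ≥ x | n, p0) is below 0.10.

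For Benchmark 2, section 9.2 says that 87% observed with N = 30 excludes 75%. At 26/30 (86.7%) the lower limit is 75.10% and the tail probability at 0.75 is 0.0979. The statement reproduces, so the convention is the one the plan used.

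**3. Benchmark 3 by the same method**

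| Observed | Proportion | Lower limit | P(X ≥ x) at 0.85 | Excludes 85%? |
|---|---|---|---|---|
| 81/90 | 90.0% | 84.67% | 0.1153 | No |
| 82/90 | 91.1% | 85.96% | 0.0632 | Yes |
| 90/100 | 90.0% | 85.01% | 0.0994 | Yes, by 0.01 point |

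The stated figure does not reproduce on its own denominator. The shortfall is 85 − 84.67 = 0.33 points.

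Other methods or levels would clear 85% at 81/90: Wilson 85.20%, mid-P 85.25%, Jeffreys 85.32%, Wald 85.95%, and Clopper-Pearson at one-sided 80% 86.36%. The plan names none of these for Benchmark 3.

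**4. The per-group target**

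Section 9.2 sets the target in each group. The same rule by arm gives:

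- n = 22: 22/22 is needed (lower limit 90.06%); 21/22 gives 83.44%.
- n = 34: 32/34 is needed (lower limit 85.10%); 31/34 gives 81.40%.

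**5. If 100 is the intended size**

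The documents give no allocation for 100. As an assumption, wave 4 becomes 100 − 66 = 34, split equally, giving 22:39:39. With 10% loss, 0.9 × 39 is about 35 evaluable in each larger arm.

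- Benchmark 1, baseline mean 2000 kcal/day: the half-width is t(0.90, 34) × 250/√35 = 1.307 × 250/5.916 = 55.2, so about 255 kcal/day (12.8%). At n = 30 the half-width is 59.9, which reproduces the plan's 260 kcal/day (13%).
- Benchmark 2: 30/35 (85.7%), lower limit 75.10%.
- Benchmark 3: 90/100, as in the table.

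**The case against.** The strongest reply is that all of this is small and hedged. The totals carry words such as approximately and anticipate, the correction is one participant, and section 9.1 says that the pilot is about feasibility rather than hypothesis tests. That stands, and it limits the weight of the point. It does not make the 81/90 statement true, because that is an exact count with a named method.

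Three stronger readings are tempting, and the documents do not support them.

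- *A trial retaining 81/90 would be declared a success although its interval includes 85%.* Section 9.5.1 computes the interval from the observed data, so 84.67% would be reported. Nothing makes 81/90 a decision rule; it is an illustration in the sample-size section, and the benchmark itself is retention above 85%.
- *The statement holds at 100 and fails at 90, so these are materially different designs.* The change is binomial discreteness. Taking the smallest count that gives at least 90% at each N from 85 to 105, the lower limit falls below 85% only at N = 90, 91 and 92. It passes at 89 (81/89, 85.81%) and again at 93 (84/93, 85.15%).
- *The forecast of 20:30:30, or 80/90 = 88.9%, shows that the plan expects to miss its own mark.* Section 9.2 describes the 30 as 10% loss. Applied to all arms, that gives 19.8 + 30.6 + 30.6 = 81, and the 80 is a rounding. Those counts are also of paired measures, whereas Benchmark 3 counts completion of the 9-month exam.

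**Conclusion.** Two separate corrections are needed, both minor. First, the Benchmark 3 figure in section 9.2 is wrong by the plan's own method: 82/90 (91.1%) is needed, not 81/90 (90%). This rests on Clopper-Pearson at one-sided 90%, pooled over 90 participants and with no clustering. The plan itself says that a large positive ICC would push the figure higher. Second, the total of about 100 randomised disagrees with the wave sizes, the arm allocation and the Benchmark 3 denominator, which all give 90. The benchmark definition and the planned analysis are unaffected; only the stated planning figures need repair. The pooled figure also does not speak to the per-group target that precedes it in the same paragraph, and correcting 81 to 82 would leave that mismatch in place.

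**What to change.** State one randomised total in the Précis and in sections 1.1, 3, 4.3, 5.1, 9.1 and 9.2.

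- **If 90:** replace the statements of about 100 with 90 (22:34:34), and restate the Benchmark 3 figure as 82/90 (91.1%, lower limit 85.96%).
- **If 100:** restate the wave 4 size, the allocation and the figures for all three benchmarks. The Benchmark 3 figure would then be 90/100, which clears 85% by only 0.01 point.

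In either case, say in section 9.2 that the Benchmark 3 figure is for pooled retention. State whether the per-group target is also to be judged by its interval, which at the current arm sizes would need 22/22 and 32/34, or is to be read from the point estimate.

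The cost of the first option is wording and a slightly less favourable retention figure (one more completer), with no added participants. The second implies about ten more than the wave 4 size now stated.
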